Background: Recurrent transcranial magnetic stimulation (rTMS) is a consolidated procedure for the treatment of depression, with several meta-analyses demonstrating its efficacy. The theta burst stimulation (TBS) method is a modification of the usual rTMS protocol, with short bursts of stimulation at high frequencies, with the bursts themselves being applied 5 times per second. As a new intervention method, there are still few studies evaluating its efficacy in treatment of major depression. However, a recently published meta-analysis has pointed to benefits of this therapeutic modality. To date, there are no studies published with this method for the treatment of geriatric depression.

Methods/design: The proposed study is designed as a double-blind clinical trial to assess the efficacy of rTMS theta-burst in the treatment of major depressive disorder in the elderly, in a sample of 108 individuals. Patients will be randomized to two groups: the experimental (TBS) and comparative (sham) group. Inclusion criteria include a diagnosis of Major Depressive Episode and a minimum age of 60 years. The coil will be positioned in the dorsolateral prefrontal cortex, with intermittent TBS mode on the left and continuous TBS on the right. There will be 20 consecutive sessions. Outcome measures will be at eight occasions: before the intervention (baseline) and after 1, 2, 4, 6, 8 and 12 weeks of onset. The main clinical result will be measured using the Hamilton Depression Scale (HDRS), comparing the initial scores with those obtained at the end of 6 weeks after the intervention. As secondary outcomes, we will use the Global Clinical Impression Scale (CGI), the CIRS (Cumulative Disease Assessment Scale), the Geriatric Depression Scale (GDS), the intermediate scores obtained on the HDRS scale and the variations in serum BDNF concentrations. As parameters of tolerability and safety, the incidence of adverse events and the occurrence of manic and / or hypomanic symptoms will also be assessed by the Young Mania Scale (YMRS).

EXPECTED RESULTS: TBS stimulation will prove to be a safe, well-tolerated and effective intervention for the treatment of major depression in the elderly, becoming a more therapeutic option, particularly useful for patients with poor response or contraindications to the use of antidepressants.

Trial registration: NCT0484292 Registered on <https://clinicaltrials.gov/ct2/show/NCT04842929>

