The coil will be positioned in the prefrontal dorsolateral cortex, with intermittent TBS (TBSi) mode on the left and continuous TBS (TBSc) on the right (F3 and F4 positions determined by the 10–20 Electroencephalographic International System). 1800 pulses will be used on each side, totaling 11 minutes 39 seconds of total duration. TBS will have the following parameters: in cTBS bursts of three pulses at 50 Hz (20-ms interval between stimuli) will be applied continuously for 120 s total in the right DLPFC and iTBS bursts of three pulses at 50 Hz (20-ms interval between stimuli) will be applied for 2-s duration repeated every 10 s for a total time of 570 s also totaling 1800 pulses in the left DLPFC, both with 120% of motor threshold. We will use a magnetic stimulator device (MagVenture©) in study mode for double-blind trials. The coil has a side that is active and the other is sham. The applicant of TMS will be blinded too (after placing the coil over the patient's head and entering his number, the device tells if the position is correct or if you have to turn it, but the applicant does not know externally what is the sham side of the coil). The sham produces the same sound as the real one. We also put on the head electrodes that give stimulus to mimic the real magnetic coil (both groups receive this). There will be

20 consecutive sessions, one per day, except on weekends and holidays, totaling around 4 weeks. A day of stimulation with the same technique will be done in the 6th week, 8th week and 12th week.

Clinical variables

We will use the MINI questionnaire for the diagnosis of psychiatric disorders, applied by an experienced psychiatrist. It is translated and validated into the Portuguese language³⁹. The demographic and clinical profile of the patients will be evaluated by: gender, age, schooling, socioeconomic status, clinical comorbidities, use and dose of antidepressants and other psychoactive drugs.

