The main outcome will be measured using the HDRS scale. The primary evaluation will be done at the end of 6 weeks from the start of the first day of TBS. As secondary outcomes we will use the GDS (Geriatric Depression Scale), Cumulative Illness Rating Scale (CIRS), the global clinical impression scale (CGI), Positive and Negative Affect Scale (PANAS), Montgomery-Asberg Depression Rating Scale (MADRS), and Edinburgh Handedness Inventory (EHI). All scales have already been translated and validated into Portuguese⁴⁰. Outcomes will be measured on 7 occasions: baseline after 1, 2, 4, 6, 8 and 12 weeks of study entry. The presence of adverse effects and the Young mania (YMRS) questionnaire will also be evaluated to detect manic and / or hypomanic cycling.

Cognitive Assessments

The cognitive battery will be applied by experienced neuropsychologists. For cognitive assessments they will be exploratory, secondary outcomes will be measured on the baseline, on the 20th day of the session and the addenbrooke cognitive examination will also be reapplied on the 12th week. We will use the Addenbrooke's Cognitive Examination - Revised Version (ACE-R), Ravlt - Word List, Rey's complex figure, Stroop Test (violet version); Wais III - Subtest Codes; Trail Making A and B and WASI - Vocabulary and Matrix Reasoning subtest.

Biomarkers

BDNF (brain-derived neurotrophic factor) is implicated in the pathophysiology of depression. Recent meta-analyses have shown that depressed patients have lower serum levels of BDNF than normal subjects^{41,42}. The samples will be collected in dry tubes, centrifuged within two hours after collection, then separate the serum and refrigerate it in eppendorfs at -70oC in liquid nitrogen. The samples will therefore be stored in a cryogenic bank. They will be collected at the beginning of the study and in the 6th week.

Cerebrospinal fluid (CSF) samples will be collected by means of a lumbar puncture during the evaluation procedures before the intervention begins. They will be used for the investigation of beta-amyloid peptide (Aβ1-42) and Tau protein (total and phosphorylated). These determinations will allow

the analysis of the interaction between the presence of Alzheimer's disease pathology and the therapeutic response to the TBS intervention.

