Actigraphy consists of a wrist device equipped with an accelerometer, a microprocessor and an internal memory, which are capable of detecting and storing the movement record. It is used in the evaluation of sleep disorders such as diseases of circadian rhythm, insomnia and excessive daytime sleepiness. We will use the actigraphy on the left wrist of the volunteers 1 week before the beginning of the research and for another 4 weeks after the study. The objective is to assess sleep changes associated with the clinical response to magnetic stimulation.

Pupil Examination (PLR) the participant will do a test lasting about 20 minutes in which a camera phone will record the size of your pupil during this period while you will hear some sounds. The exam is painless and without side effects.

Sample size calculation:

Based on the clinical trial of Li⁴³, which demonstrated an efficacy favoring bilateral TBS in depression of 52.5% for the active group and 17.4% for the sham group, for a two-tailed p 0.05 and a power of 90%, the total sample size is 86 subjects. Considering a rate of friction of approximately 25%, we estimated the final sample size in 108 patients.

Statistical analysis

Statistical analysis will be performed with the Stata 16 SE program for Mac OS X. All analyzes will be made on the intention to treat principle (ie the data of all participants will be included in the analysis) in which lost data will be allocated according to the last observation carried forward principle and/or mixed data. Analyzes will be considered significant at p <0.05. We will use parametric tests to analyze the main outcomes, which are allowed by the sample size. Number of previous admissions, presence of clinical comorbidities, refractoriness (measured by the Massachusetts General Hospital scale - MGH-S)⁴⁴ will be analyzed as ordinal data. For the main outcome we will use a repeated measures analysis, having HDRS scores as Dependent variable and TBS as independent variable at week 8. Secondary analyses of the other scales and biomarkers will be performed in the same way, replacing HDRS as a dependent variable.

Study Flow Chart

We show below the flowchart for each patient throughout the study. It is worth remembering that TBS will be applied 23 times: 20 consecutive sessions (week 0 through week 4), 6th week, 8th week and 12th week. Still, patients who receive *sham* stimulation and who are still depressed may receive active stimulation at the end of the study.

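### The primary HDRS endpoint is at week 6 in the Methods but is analysed at week 8 in the statistical section, so the plan fixes no single primary test

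*Combined protocol and SAP*

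**What the plan says.** Three places in the combined protocol and SAP give a time for the main HDRS result.

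- **Clinical variables:** "The primary evaluation will be done at the end of 6 weeks from the start of the first day of TBS".
- **Statistical analysis:** the main outcome is analysed by repeated measures, "having HDRS scores as Dependent variable and TBS as independent variable at week 8". This is the only time point in that section.
- **Abstract, Methods/design:** the main result is obtained by "comparing the initial scores with those obtained at the end of 6 weeks after the intervention".

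The visit calendar is the same throughout. The abstract lists follow-up "after 1, 2, 4, 6, 8 and 12 weeks of onset". Clinical variables says "Outcomes will be measured on 7 occasions: baseline after 1, 2, 4, 6, 8 and 12 weeks of study entry". Table 1 gives weeks 6 and 8 separate columns, each with a clinical interview and a stimulation session.

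The significance level is 0.05, with no rule for testing more than one time point.

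**The concern.** The Methods and the statistical section both speak about the primary outcome and name different visits. The statistical section is the text an analyst will execute, and executed literally it tests week 8.

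The two visits also ask different questions. One falls about two weeks after the daily course ends and the other about four weeks after, with further stimulation scheduled on that stretch.

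With two primary time points written down in advance, the reported one can be picked after the results are known. The 5% error rate then no longer applies. Even if the team acts in good faith, a critic can point to the visit that was not reported and allege selective reporting.

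**Working it through.** **1. Is it only a difference in where counting starts?** No. The abstract counts visits from onset, Clinical variables from study entry, and Table 1 uses the same week numbers. On that scale week 8 is the visit after week 6, not another label for it.

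**2. How far apart are the two visits in treatment terms?** Interventions gives "20 consecutive sessions, one per day, except on weekends and holidays, totaling around 4 weeks" and then "A day of stimulation with the same technique will be done in the 6th week, 8th week and 12th week".

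- Week 6: 6 − 4 = about 2 weeks after the daily course.
- Week 8: 8 − 4 = about 4 weeks after it.
- If assessment and stimulation come in the same order at both visits (the document does not give the order), one further stimulation day falls between the two assessments.

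**3. What does the abstract mean?** Counted from the end of the course, its six weeks would be 4 + 6 = about week 10, when no visit is scheduled. Counted from onset, as the abstract counts its visits, it is week 6. The second reading is the workable one, but the wording does not exclude the first.

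**4. Does the rest of the plan favour one visit?** The statistical section applies the same analysis to the biomarkers. On serum samples, the Biomarkers section says: "They will be collected at the beginning of the study and in the 6th week". Table 1 agrees. A week-8 analysis of BDNF is therefore impossible. This points towards week 6 as the intended time but does not prove it.

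**5. Does the choice of visit affect the sample size?** The plan's figure is 86 in total, from 52.5% against 17.4%, two-sided 0.05 and 90% power. I assume 1:1 allocation, with p̄ = (0.525 + 0.174)/2 = 0.3495.

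- Uncorrected, per arm: n = [1.960·√(2·0.3495·0.6505) + 1.282·√(0.525·0.475 + 0.174·0.826)]² / 0.351² = (1.3216 + 0.8035)² / 0.1232 = 36.66.
- With continuity correction: (36.66/4)·[1 + √(1 + 4/(36.66·0.351))]² = 42.16, so 43 per arm and 86 in total.

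The stated figure is reproduced. The two rates carry no time point in the document, so choosing week 6 or week 8 changes no stated planning input.

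**6. What would a free choice between the visits cost?** Let Z₆ and Z₈ be the test statistics at the two visits. Under the null hypothesis, treat them as bivariate normal with correlation ρ. The chance that at least one is significant at two-sided 0.05 is

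1 − P(|Z₆| ≤ 1.96 and |Z₈| ≤ 1.96).

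| Assumed ρ | P(neither significant) | False-positive rate |
|---|---|---|
| 0.6 | 0.9125 | 8.75% |
| 0.7 | 0.9165 | 8.35% |
| 0.8 | 0.9219 | 7.81% |
| 0.9 | 0.9296 | 7.04% |

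The document gives no correlation, so the range is an assumption. For reference, independent tests would give 1 − 0.95² = 9.75%. The rate exceeds 5% at every correlation below 1.

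**The case against.** **It is a slip of the pen.** The two places that define the outcome both name six weeks, and the biomarker schedule cannot support week 8. A drafting error is the likeliest explanation. That does not remove the conflict, because the slip sits in the section that governs the analysis and nothing says which text prevails.

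**A repeated measures model may simply run through week 8.** On that reading there is no single-visit test at week 8, and the two-test calculation does not describe the model. The ambiguity is real. But the section names no week-6 contrast, so the mismatch with Clinical variables remains and the text still needs amending.

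**The abstract is not a true third time point.** This largely stands. Read with its own visit list, the abstract agrees with week 6. It is a wording repair, and the finding does not depend on it.

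**The inflation figure is conditional.** This also stands. It applies only if both visits are examined and the favourable one is reported, which the plan does not propose. It also counts errors in either direction. A false claim that active stimulation beats sham would occur about half as often: roughly 3.5% to 4.4%, against a nominal 2.5%.

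**Changing one phrase does not complete the primary test.** Correct. The section does not say whether the test is the group effect, the group-by-time interaction or a contrast at one visit, and it leaves the missing-data method as a choice between last observation carried forward and a mixed approach. The amendment should deal with these points too.

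**Conclusion.** The contradiction is real and must be fixed. The Methods set the primary HDRS evaluation at week 6 from the first session, and the statistical section analyses it at week 8. These are different scheduled visits, and nothing reconciles them.

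If either could be declared primary at 0.05, the two-sided false-positive rate would be 7.0% to 8.8%. That rests on bivariate normal test statistics, an assumed correlation of 0.6 to 0.9, and selection after the results are seen. The contradiction itself rests on the text alone and needs none of these assumptions. The sample size is not affected.

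**What to change.** Before anyone sees outcome data by arm:

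1. In Statistical analysis, replace the reference to week 8 with week 6 counted from the first TBS session, and name the between-group HDRS contrast at that visit as the primary test.
2. Put the same time point, with the same starting point for counting, in the abstract.
3. State that HDRS at weeks 1, 2, 4, 8 and 12 is secondary.
4. In the same edit, choose one missing-data method for the primary test, so that it is fully determined.

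Week 6 is the natural choice because it is the explicit definition in Clinical variables and matches the blood sampling. If the team did intend week 8, it should say so and amend Clinical variables, the abstract and the biomarker analysis instead.

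The cost is a short dated amendment to the text. HDRS is already scheduled at both visits, so no visits, procedures or patients are added.

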The randomization will be in block, in which there will be permutation in the order and size of the blocks. The randomization will be generated through the website www.randomization.com by a researcher who will not be directly linked to the research. Patient allocation will be done through sealed, opaque and standardized envelopes. After the patient signs the informed consent form, the envelope will be opened and the envelope will be allocated to the treatment, in a coded form. The envelope will be identified with a random number that will be assigned to each patient.

Inclusion and exclusion criteria

Patients older than 60 years, with initial HDRS greater than 17, who have MDD. The exclusion criteria will be: other mental disorders (alcohol or drug addiction, psychotic disorders, dementia, bipolar disorder); presence of serious neurological or clinical diseases; presence of severe suicidal ideation and CIRS (Cumulative Illness Rating Scale) score > 7, characterizing a set of clinical morbidities that could impair adherence to the research protocol. In addition, specific contraindications to the use of rTMS will also be excluded, such as: metal implants, epilepsy or electronics in the cephalic segment. Patients who are receiving antidepressants will have a wash-out of five half-lives of the medications prior to entry into the study. Patients receiving benzodiazepines will be included since receiving a maximum dose of 10mg of diazepam or equivalent. Other psychoactive drugs will be accepted as long as the doses of the medications have been stable for at least 6 weeks.

Blinding

The study will be double-blind, evaluators and patients will not be aware of the randomized treatment until the end of the study. The blinding will be done with a sham coil, which consists of a coil that reproduces the sound that the true coil does, but without generating the magnetic field. A person only intended to apply the rTMS session will do the procedure and will not be involved with the evaluations or with the evaluators, this person will be also blinded. A blinding scale will be applied to evaluators, applicators, and volunteers to evaluate if the blinding was effective.

Interventions

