Here we provided the study protocol of a randomized controlled trial (RCT) that will evaluate the efficacy of TBS for the treatment of geriatric depression. To the best of our knowledge, this is the first study in this field. The participants will receive 23 sessions of bilateral TBS, comprising first inhibitory stimulation delivered by cTBS in the right DLPFC followed by excitatory stimulation delivered by iTBS in the left DLPFC, totalizing 3600 pulses. We performed sample size calculation based on the effect size found in the most similar clinical trial found in literature⁴⁵. There are no specific treatments using neuromodulation for depression in the elderly. This study aims to answer this question. We will enroll patients with different degrees of refractoriness and the TBS as the only treatment for depression (the antidepressants will be wash-out). , which will significantly increase the external validity of our results. These data could contribute to the analysis of some predictors of response as well.

We expect that TBS will be statistically superior to sham treatment for depression as assessed through the Hamilton Depression Rating Scale (HDRS). Other expected secondary outcomes consist of: TBS will be superior to sham treatment for improvement of depressive symptoms by the GDS (Geriatric Depression Scale), the MADRS (Montgomery-Asberg Depression Rating Scale), and the Global Clinical Impression Print Scale (CGI). Regarding serum markers, we expect that the TBS group active vs. sham will show a significant increase in BDNF levels. From the neurocognitive point of view, we expect that both groups will perform similarly.

Conclusions

This study will investigate the efficacy of TBS for the treatment of major depressive disorder in elderly patients using a randomized, sham-controlled design. The biomarker investigation will contribute to the understanding of the neurobiological mechanisms of depression and their relationship with the treatment. This trial will contribute valuable information to the treatment of depression in the elderly.

Author's contributions:

LV is responsible for initiating and managing the trial, conceived and designed the essay, analyse the data and wrote the manuscript. PJCS, WG, AB, OF performed the statistical analyzes, LS, RB, CM, JL are responsible for the clinical evaluation.LT, HC, RV, RM responsible for the neuropsychological evaluation. PO responsible for the collection of CSF, KM responsible for collecting

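### The primary HDRS model names treatment as its only independent variable and does not prespecify adjustment for baseline HDRS, which costs precision by an amount that depends on assumptions

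*Combined protocol and SAP*

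**What the plan says.** The Statistical analysis section introduces the primary model with "For the main outcome we will use a repeated measures analysis" and completes it with "having HDRS scores as Dependent variable and TBS as independent variable at week 8". It gives no time terms, covariance structure or covariates. The other scales and the biomarkers are to be analysed the same way.

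Baseline HDRS is available for everyone. It is an entry criterion (Inclusion and exclusion criteria: "Patients older than 60 years, with initial HDRS greater than 17, who have MDD") and the first measurement occasion (Clinical variables: "Outcomes will be measured on 7 occasions: baseline after 1, 2, 4, 6, 8 and 12 weeks of study entry"). The abstract describes the main result as "comparing the initial scores with those obtained at the end of 6 weeks after the intervention".

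The Statistical analysis section also lists "refractoriness (measured by the Massachusetts General Hospital scale - MGH-S" among variables to be treated as ordinal, without naming a model that they enter. The randomisation section describes permuted blocks and states no stratification factor.

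**The concern.** Baseline severity usually predicts later severity on the same scale. A primary model that does not use it as a covariate, or constrain the arms to a common baseline mean, gives a wider confidence interval than the same data could support. With about 54 patients per arm and no stated stratification, some chance imbalance in baseline HDRS is to be expected. A post-score comparison leaves that imbalance in the estimate, and a change score over-corrects for it.

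Prespecification is also at stake. The text fits a post-score contrast, a change-score contrast, or a longitudinal model with baseline among the responses. These differ in precision and can give different p-values on one dataset, so the choice should not remain open at unblinding.

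**Working it through.** **The plan's own figure.** The stated rates of 52.5% and 17.4%, two-sided 0.05 and 90% power give 43 per arm, or 86 in total, with a continuity-corrected two-proportion formula. This matches the plan. Then 86 × 1.25 = 107.5, rounded up to 108. The calculation is for proportions, so it supplies no HDRS standard deviation, mean difference or correlation. The loss below cannot be derived from the documents alone.

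**Inputs**
- From the plan: 108 patients and 25% loss, so 108 × 0.75 = 81 evaluable.
- Assumed: 1:1 allocation (40.5 per arm); correlation r between baseline and follow-up HDRS of 0.2 to 0.5; equal standard deviations at both visits; true standardised difference d of 0.6 or 1.0.
- The value 1.0 is what the planning rates imply if they are responder rates from cutting a normal score at a threshold: z(0.525) − z(0.174) = 0.063 + 0.938 = 1.00. The value 0.6 is a more cautious illustration and is not in the documents.

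**Variance of the arm difference, with the post-score comparison as 1**
- Change score, or unconstrained group-by-time contrast with baseline as a response: 2(1 − r)
- Baseline-adjusted: 1 − r²
- Adjusted relative to change: (1 − r²) / [2(1 − r)] = (1 + r)/2

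| r | Adjusted / post | Saving | Adjusted / change | Saving |
|---|---|---|---|---|
| 0.2 | 0.96 | 4% | 0.60 | 40% |
| 0.3 | 0.91 | 9% | 0.65 | 35% |
| 0.5 | 0.75 | 25% | 0.75 | 25% |

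A simulation of complete data with 43 per arm and r = 0.3 gave standard errors of 0.2136 (post), 0.2496 (change) and 0.2041 (adjusted). The variance ratios are 0.2041²/0.2136² = 0.91 and 0.2041²/0.2496² = 0.67, in line with the formulas.

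**Power.** Two-sample t-test, two-sided 0.05, 40.5 per arm, with d divided by 1, √[2(1 − r)] or √(1 − r²):

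| d | r | Post | Change | Adjusted |
|---|---|---|---|---|
| 0.6 | 0.3 | 76.0% | 61.6% | 79.8% |
| 0.6 | 0.5 | 76.0% | 76.0% | 86.9% |
| 1.0 | 0.3 | 99.4% | 96.4% | 99.7% |

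At r = 0.3 and d = 0.6 the gain is 79.8 − 76.0 = 3.8 points over post scores and 79.8 − 61.6 = 18.2 over change scores. At d = 1.0 it is 0.3 and 3.3 points.

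**Which r is plausible.** The HDRS entry threshold narrows the baseline range and lowers r. With an assumed unrestricted baseline mean of 20 and SD of 5, keeping only values above 17 takes correlations of 0.3 and 0.5 down to about 0.22 and 0.38. At the low end, the gain over post scores is small and the gain over change scores is large. If the threshold also makes baseline less variable than follow-up, the equal-SD assumption fails and the change-score penalty is smaller. With k the ratio of baseline to follow-up SD, the excess of change over adjusted variance is (1 + k² − 2rk) − (1 − r²) = (k − r)², which is never negative.

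**The case against.** A reader might infer that the plan excludes baseline HDRS. The text does not support that. The analysis is called repeated measures, baseline is one of the seven occasions, and the abstract compares initial with later scores, so baseline may already be among the responses. If the model also held the arms to a common baseline mean, it would recover essentially all of the gain from adjustment. This objection stands against any claim of exclusion. It does not remove the point, because the plan states no such constraint, and without it the arm-by-time contrast has the change-score variance.

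The power figures come from single-visit t-tests, not the planned longitudinal model, and rest on an effect and a correlation that the documents do not give. At the effect implied by the planning rates, the loss at r = 0.3 is 3 points at most. The plan also intends to include all participants through last observation carried forward. Counting all 54 per arm, power at d = 0.6 and r = 0.3 is 87.1% (post), 74.2% (change) and 89.9% (adjusted). All of this stands, and it is why the loss is given as a range.

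A reader might also infer that leaving out refractoriness wastes precision. The Discussion says "We will enroll patients with different degrees of refractoriness" and "These data could contribute to the analysis of some predictors of response as well", which shows an interest in predictors, but no section gives the prognostic value of the MGH-S score. Its role is unstated, and any gain from it would be an assumption.

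**Conclusion.** The point holds as a gap in efficiency and prespecification. Treatment is the only independent variable named, baseline HDRS is in hand for every patient, and no baseline-adjusted or common-baseline-mean model is specified. It would be wrong to read this as bias: under randomisation the unadjusted contrast remains unbiased with a valid type I error.

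The variance saving is 4 to 25% against post scores and 40 to 25% against change scores for r from 0.2 to 0.5, given equal standard deviations. The power gain at r = 0.3 with 81 evaluable patients is about 4 to 18 points at a standardised difference of 0.6 and 0 to 3 points at 1.0. The upper figure in each range applies only if the analysis turns out to be a change-type contrast, which the abstract's wording allows but does not settle. The change should be made because it is nearly free, even though the size of the loss is uncertain.

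**What to change.** Before unblinding, state the primary model as a linear mixed model on post-baseline HDRS (weeks 1, 2, 4, 6, 8 and 12) with arm, visit, arm-by-visit, baseline HDRS and baseline-by-visit. An equivalent choice keeps baseline among the responses and constrains the arms to the same baseline mean. Report the arm difference, with its confidence interval, at one primary visit. That requires reconciling week 6 (abstract and Clinical variables) with week 8 (Statistical analysis). Carry the same structure over to the secondary scales that are to be analysed in the same way, using each scale's own baseline and visits.

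The MGH-S score may be added if the investigators judge it prognostic, provided this is decided in advance. The cost is SAP wording only: no new data and no extra patients.
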